#### **Lay Abstract**

The Caribbean region has high rates of HIV. The majority of these are found on Hispaniola, an island made of the Dominican Republic (DR) and Haiti. Due to a large international response and availability of treatment, the number of new HIV infections in the DR has gone down and about 1% of the general population is living with HIV. The effective management of this condition depends on those living with HIV being able to access treatment and apply the information and skills that improve adherence. Unfortunately, in developing countries such as the DR, many things make it more difficult for individuals to get and use this information. Health care providers can help patients understand health information by offering it in targeted, culturally-, and literacy-appropriate ways, such as by using images that contain information e.g. infographics. When well designed, infographics can support communication in culturally friendly and visually appealing ways. This can improve understanding, health behaviors, attention span, and ability to remember information. In earlier studies, a set of infographics was developed from input from patients and providers. This next study phase is to test if these infographics are a useful method to improve communication and lead to better health for patients. Additionally, understanding the cultural factors that change clinician-patient communication using infographics in a clinical setting will provide valuable information as to how to improve clinical communication with this population.

#### **Risks, Benefits, and Monitoring**

##### **Potential Risks**

One potential risk to participants directly related to their participation in this protocol is possible loss of confidentiality. However, all of the data safety and monitoring procedures in this protocol will be strictly adhered to in order to avoid any loss of confidentiality. An additional risk is that participants might feel uncomfortable if they are unable to answer some of the questions in the surveys. Prior to beginning data collection, all participants will be reminded they do not have to answer any question that makes them feel uncomfortable and that they may withdraw from the study at any point without any consequences whatsoever. During the study visits, a study team member will also be available in order to provide any help that does not lead participants to the correct answer. During in-depth interviews participants may feel discomfort discussing their HIV status. Prior to interviews, participants will be reminded that they do not have to answer any question that makes them feel uncomfortable and that they are free to leave the interview at any time without any consequences whatsoever.

Additionally, all study team members will be trained to identify signs of suicidal ideation and depression. Should they notice any of these signs while they are completing a study visit, or if participants are showing signs of discomfort, the study visit will be stopped immediately and the participant will be referred to speak to the on-site psychologist.

##### **Potential Benefits**

This study does not have any direct benefit to participants. However, participants are more likely to benefit from the health education provided through their visits because of the intervention. Additionally, by participating in this research, they will be able to actively contribute to improving the health care services that they and their peers receive.

#### Alternatives

This study does not present greater than minimal risks to participants. However, an alternative is to not participate in this research.

#### Data and Safety Monitoring

The safety of this study's data will be regularly monitored by the study team. Any breaches of the study protocol will be submitted to the IRB immediately.

#### Subjects

##### Study population characteristics

This study will enroll adult ( $\geq 18$  years of age) patients at Clínica de Familia La Romana who are living with HIV, have detectable viral loads, and are planning to receive care at the clinic for the next year. Participants are likely to be economically and educationally disadvantaged and non-English speaking.

##### Subject population justification

PLWH at Clínica de Familia La Romana have low levels of education and low health literacy  and adherence to antiretroviral medications is a perpetual concern. Although a vulnerable population because they are living with a stigmatized health condition and are economically and educationally disadvantaged, their participation in this research is justified because it enables them to help design a tool and intervention that may help them to better manage their condition and improve the clinic services that they and their peers receive. Furthermore, if the target population of interventions is not included in the research design and evaluation phases, interventions may be ineffective and misguided.

##### Describe and justify reimbursement/compensation

Participants will receive money for transportation (\$3) to each of their study visits (four visits total). Participants who participate in the in-depth interviews will also receive \$3 for that visit. Providers involved in the intervention will be provided a small incentive (\$50) for completing the training on how to administer the intervention and a small incentive (\$50) following the semi-structured interview that they will complete at the end of the study.

## Statistical analysis plan

Sample size estimation was based on the recommendation of having 35-40 participants to pilot test instruments, thereby estimating the associated treatment effects. To account for 20% attrition (2% over the average rate in health behavior change trials to account for difficulties in retention associated with this population), 50 participants were recruited. Adults ( $\geq 18$  years of age), living with HIV, with a detectable viral load ( $\geq 40$  copies/mL) on their most recent laboratory test, who were planning to receive care at the Clinic during the study period, were eligible to participate.

We first characterized the study sample using descriptive statistics. Means and standard deviation and frequency analysis were performed on baseline demographic characteristics. Next, descriptive statistics of all outcome measures were performed, stratified by time point (baseline, 3-, 6-, and 9-months). Means and standard deviations were then computed for outcomes that roughly follow normal distribution and median and interquartile range were computed for skewed variables. So as not to inflate type II error, statistical analyses were only conducted for a subset of outcome variables, selected based on our theoretical model. The variables analyzed were: HIV-related knowledge, self-efficacy to manage HIV, CD4 count, viral load, current health status, and engagement with clinicians. Descriptive statistics of the remaining outcome variables were calculated.

To determine appropriate tests of association, tests for normality were conducted on all variables. If they were skewed, we log transformed variables to determine if skewness improved. The variables that met normality assumptions were then analyzed using general linear regression and those that were heavily skewed were analyzed using Wilcoxon signed-rank tests.

General linear regression with generalized estimation equations (GEE) with robust standard errors were conducted with the following continuous dependent variables: HIV-related knowledge, self-efficacy to manage HIV, CD4 count, and viral load measured at each time point. GEE was used to account for the clustering effect of repeated measures. This analysis allowed us to estimate how scores on outcome measures changed from baseline to follow up visits (at 3-, 6-, and 9-months). Independent variables included in each regression model were if participants were new patients at the time of enrollment and time (baseline, 3-, 6-, and 9-months). If participants were new to the clinic was represented by a dichotomous yes/no variable where “yes” indicated a participant had been attending the clinic for less than 3 months at the time of enrollment, as that is the time it takes to see changes as a result of ART treatment. The only variable where log transformation improved normality was viral load, so log transformed viral load was used in that regression model. Histograms of the residuals from final regressions were evaluated again for normality following tests to verify the normality assumptions were met.

Wilcoxon signed-rank non-parametric tests of association were used to compare the outcome measures current health status and engagement with clinician at baseline with those obtained at the follow up time points as initial analyses demonstrated these variables did not meet normality assumptions. This analysis enabled us to establish if the changes seen at different time points in the longitudinal study were statistically significantly different than those obtained at baseline.

Because this is a preliminary pilot test with a small sample size, we wanted to detect any interesting findings, we did not adjust for multiple comparisons in the regression models. In the applied sciences, it is considered appropriate to not adjust for multiple comparisons when the tests are planned, especially when there are only a few tests. However, we did use the conservative Bonferroni correction adjustment for multiple comparisons for the Wilcoxon Signed-Rank tests when assessing the outcome measures current health status and engagement with clinician, as we ran each test three times to compare scores on baseline assessments to those at 3-, 6-, and 9-month follow up visits. Therefore, the Wilcoxon signed-rank tests were considered significant if  $p \leq 0.05/3 = .017$ .

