Preliminary studies (T32 NR013454) showed many persons living with HIV (PLWH) attending Clínica de Familia La Romana do not fully comprehend and use the health information they receive through current modalities. In response, culturally relevant, evidence-based infographics to improve information delivery during clinical visits were developed (T32 NR007969) with a participatory design methodology (manuscript under review). The next phase of this study is to rigorously assess if using these infographics is a feasible, acceptable, and efficacious method to enhance HIV-related clinician-patient communication and lead to improved patient outcomes. Additionally, a thorough exploration into the cultural factors of patient-provider communication in the Dominican Republic that can influence infographic use for clinician-patient communication in a clinical setting is warranted.

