Participant eligibility will be verified in the medical records of patient's scheduled appointments at the beginning of each day. Eligible participants will then be recruited by the receptionist when they present to the Clinic for their regular clinic visit and referred to speak to an on-site researcher who will further introduce the study (see attached recruitment script) and then if a participant is interested, complete the informed consent process. After completing the informed consent process, participants will complete a baseline assessment using REDCap software with the help of a study team member prior to their visit (Table 1). Participants will then receive the intervention during the enrollment visit and at three and six-month visits and complete the follow up assessment at each of these time. Time intervals were selected as CD4 count and viral load may change as early as three months after ART initiation. Interventionists will time visits and no extra time will be allowed for study visits. Following their six-month study visit, participants will be asked to participate in in-depth interviews. At the nine-month study visit, participants will complete a follow up assessment to assess ability to recall information from infographics over time. At the end of the study, the interventionists will be interviewed to assess feasibility of infographic use in a clinical setting.

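### New-patient status enters the viral load and CD4 models only as a fixed level shift, so new patients' ART response stays in the change estimates and these cannot serve as the infographic effect of Aim 3

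*SAP*

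**What the plan says.** The GEE paragraph of the SAP covers four outcomes: HIV-related knowledge, self-efficacy, CD4 count and log-transformed viral load. On covariates it says: "Independent variables included in each regression model were if participants were new patients at the time of enrollment and time". Neither document lists an interaction, a stratified analysis, an ART start date or time on ART.

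A patient is new if he or she had attended the clinic for under 3 months at enrollment. The SAP justifies the cut-off by ART: "as that is the time it takes to see changes as a result of ART treatment". The Protocol (Intervention) says likewise that "CD4 count and viral load may change as early as three months after ART initiation".

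The SAP describes the model output as change: "This analysis allowed us to estimate how scores on outcome measures changed from baseline to follow up visits". Other places use the language of effect. Aim 3 is to measure what infographic use does to treatment outcomes, and Research Question 3 asks how much it influences them. The Study Purpose and Rationale sets out to "rigorously assess if using these infographics is a feasible, acceptable, and efficacious method", and the SAP's sample-size paragraph speaks of "thereby estimating the associated treatment effects".

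The Protocol gives a single-group pretest-posttest design (Study Design) and names CD4 count and viral load as primary outcomes (Measures). The SAP requires a detectable viral load "on their most recent laboratory test".

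**The concern.** The SAP ties its one patient-level covariate to the time ART takes to act, so a reader will assume that the models have adjusted for ART response. The listed form cannot do this. A patient who has recently started ART differs from an established patient in the course of viral load and CD4 count after enrollment, not only in the average level, and a fixed shift leaves that course untouched.

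These coefficients are the only model-based evidence on the primary outcomes, and the SAP leaves the regression models unadjusted for multiplicity. If new patients are a sizeable share and respond to ART, the models can show a significant improvement when the infographics do nothing. That result could then be offered as the answer to Aim 3 and carried into later efficacy testing.

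**Working it through.** **Inputs from the documents.** 50 recruited; target 35 to 40; attrition 20%; covariates new-patient status and time; visits at baseline, 3, 6 and 9 months. The sample size reproduces: 40/(1 − 0.20) = 50. The expected number of completers is 50 × 0.80 = 40, used as n below.

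**Inputs not in the documents, so assumed.** Share of new patients p; their ART response d; within-person SD s (0.6 log10 for viral load, varied from 0.3 to 0.9; 60 to 100 cells for CD4). The true infographic effect is zero and established patients are flat.

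**Step 1: algebra.** The listed model is E(y) = b0 + b1·new + c_t, with c_t = 0 at baseline. Change from baseline is (b0 + b1·new + c_t) − (b0 + b1·new) = c_t, so b1 cancels. With complete data the estimate of c_t is the pooled mean change:

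c_t = (1 − p) × change in established + p × change in new.

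Under the assumptions this is −p·d for viral load. GEE fits to simulated complete data (n = 40, 12 new) gave −0.2695, −0.3019 and −0.2422 at the three visits both with and without the new-patient term. The differences were below 1e-15, under exchangeable and independence working correlation.

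**Step 2: dropout.** The exact identity needs complete data. With n = 50, 15 new and a 2 log10 fall, equal 20% dropout gave a mean 9-month coefficient of −0.59 to −0.61 with and without the term. Dropout that differed by new-patient status shifted the mean by up to 0.04 (exchangeable) or 0.16 (independence); the SAP does not name the working correlation. In every dropout setting the coefficient with the term stayed between −0.48 and −0.64, although the infographic effect was zero.

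**Step 3: how often this looks significant.** The robust SE is about sqrt{[2s² + p(1 − p)d²]/n}. For p = 0.30, d = 1, s = 0.6: sqrt[(0.72 + 0.21)/40] = 0.152. The coefficient −0.30 is then 1.97 SEs from zero, so about half of trials reject. Simulated rejection at 9 months (uncorrected robust SE, z = 1.96):

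| Share new | Fall in new (log10) | Coefficient | Significant |
|---|---|---|---|
| 0% | none | 0 | 6% |
| 5% | 1 | −0.05 | 7% |
| 10% | 1 | −0.10 | 11% |
| 20% | 1 | −0.20 | 27% |
| 30% | 1 | −0.30 | 51% |
| 30% | 2 | −0.60 | 94% |

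Raising the SD from 0.3 to 0.9 moves the 10%, 1 log10 row from 20% to 8% and the 30%, 1 log10 row from 94% to 29%. For CD4, 10% new with a 50-cell gain gives +5 cells and 6 to 7% significant. With 30% new and a 100-cell gain it gives +30 cells and 25 to 52%.

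**Step 4: precision if the groups are separated.** 95% half-widths for 9-month viral load change (n = 40, s = 0.6, d = 1), using t with k − 1 degrees of freedom:

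| New / established | All 40 | Established | New |
|---|---|---|---|
| 12 / 28 | 0.31 | 0.33 | 0.53 |
| 8 / 32 | 0.30 | 0.30 | 0.68 |
| 4 / 36 | 0.29 | 0.29 | 1.24 |

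For CD4 (12 new, 100-cell gain, SD 60 to 100), 31 to 47 cells for all becomes 33 to 54 (established) and 53 to 88 (new). Uncorrected z intervals are too short: they miss the truth in 6% of trials for 28 established, 9% for 12 new and 19% for 4 new. The t-based ones miss in 4 to 7%.

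**The case against.** The strongest reply is that the SAP makes no analysis error on its own terms. It says that the models estimate change from baseline, and they do. No sentence calls a time coefficient an infographic effect, the treatment-effect wording sits in the sample-size rationale, and the study is openly a single-group preliminary pilot. Without a comparator the coefficient would not be the infographic effect even if no patient were new.

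All of that is true, and it fixes where the fault lies: in using these coefficients to answer Aim 3 and Research Question 3, not in computing them. The pilot label is not a caution against that use.

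The second reply is that an interaction does not rescue the design. This also stands. Established patients were enrolled on a detectable most recent test, so regression to the mean remains in their group. Suppose 36 established patients fall by 0.2 log10 for that reason alone. The estimate is then 0.2/(0.6 × √2/√36) = 1.41 SEs from zero, significant in about 29% of trials. Clinic tenure is also only a proxy for ART start. The split is therefore informative but secondary to the wording.

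The third reply is that the magnitude is wholly assumed and near nominal at 5 to 10% new. That is right, and it is why the number of new patients must be reported.

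**Conclusion.** The concern holds. With complete data the listed new-patient term has no influence on the 3-, 6- and 9-month change coefficients. With dropout it can move them, but it does not remove an ART response. This follows from the model and needs no assumption about the data beyond the additive reading of the SAP's covariate list, which is the natural one.

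The size in this trial cannot be determined from the documents. It is the share of new patients times their response: small if few are new, and large enough to produce a significant viral load fall in about half of trials or more at 30% new under the central SD. Those rates rest entirely on the assumed shares, responses and SDs. The pooled coefficients remain valid as average change, but they cannot support a statement about what infographic use did.

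**What to change.** **(a) Wording, needed whatever (b) shows.** State Aim 3 and Research Question 3 results as within-person change after exposure. Name the causes that the design cannot remove: ART response, and regression to the mean from selecting on a detectable most recent viral load. Report the number of new patients.

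**(b) Model.** Add a new-patient by time interaction to the viral load and CD4 models. Report the three changes separately for established and new patients, with the number in each group and t-based 95% confidence intervals: the group's robust SE times sqrt(k/(k − 1)), with t on k − 1 degrees of freedom, where k is the number of patients in the group seen at that visit. Label neither group's change as the infographic effect. If new patients are very few, give their estimate as descriptive only. The SAP is written in the past tense, so label the split post hoc if the main analysis has been run.

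**Cost.** Report and SAP wording, plus three extra terms in each of two models, on data already collected. The price is the wider intervals in Step 4, above all for new patients: with only 4 of them the interval is uninformative. The split also adds comparisons to an analysis where the SAP says "we did not adjust for multiple comparisons in the regression models".
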